TITLE: Transcranial Direct Current Stimulation for Freezing of Gait in Parkinson's Disease

VERSION NUMBER: 3

VERSION DATE: 9/2/2016

PROTOCOL NUMBER: 20140127

INVESTIGATOR NAME: [name]

NCT NUMBER: NCT02266004

1) Protocol Title

Transcranial Direct Current Stimulation for Freezing of Gait in Parkinson's Disease

2) IRB Review History

N/A

3) Objectives

The goal of this research is to quantify the effects of unilateral anodal transcranial direct current stimulation (tDCS) in patients with Parkinson's Disease (PD) and freezing of gait (FOG). We will test the effects of unilateral transcranial direct current stimulation (tDCS) in combination with locomotor training.

Aim1. Quantify the effects of tDCS on freezing of gait in patients with PD. tDCS will be administered together with locomotor training to patients with PD and with FOG. Temporal and spatial gait kinematics will be measured using a portable accelerometer-based system. The primary outcome will be gait velocity. Secondary outcomes will be Timed Up and Go Test (single and dual-task), the freezing of gait questionnaire, Unified Parkinson Disease Rating Scale (UPDRS), and percentage time spent with FOG during the timed up and go (TUG), and postural sway while standing (single and dual-task).

Aim2. Quantify the effects of anodal direct current stimulation on cortical excitability of the motor cortex. Effects of anodal tDCS will be assessed in patients with PD and with freezing of gait. Transcranial magnetic stimulation (TMS) will be used to probe cortical excitability and plasticity of motor cortex pre and post intervention.

Aim3. Evaluate the cortical/subcortical changes induced by tDCS. We will use magnetic resonance spectroscopy (MRS) to identify changes in brain glutamate and GABA in patients with PD and FOG.

4) Background

The neurological mechanisms underlying gait dysfunction and in particular freezing of gait (FOG) are unknown, but it is thought that impaired gait automaticity may cause patients with Parkinson's Disease (PD) to rely more heavily on cortical control for locomotion. It has been postulated that interventions that restore the normal excitability of the motor cortex would be associated with better motor function ¹(1). Noninvasive techniques such as transcranial direct current stimulation (tDCS) have been employed in various neurological conditions to modulate the cortical excitability and with improved functional outcome.

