Studies of transcranial direct stimulation suggest that tDCS improves function presumably by activating central neuromodulatory mechanisms ²(2) and spinal locomotor pattern generating circuitry ³(3). The current proposal seeks to combine tDCS and locomotor training to assess effects in walking in patients with PD. tDCS decreases the threshold for neuronal excitability and has neuromodulatory effects on cortical and subcortical structures improves the motor and cognitive functions in PD ⁴(4). We hypothesize that tDCS in combination with locomotor training will reduce freezing of gait. The effects on cortical excitability will be quantified using TMS and neurotransmitter changes associated with this intervention will be explored using MR spectroscopy.

The long-term goal of this project is to develop strategies for persons with PD that will facilitate optimal restoration of walking function. These studies are significant in that they will advance the field as relates to: 1) development of optimal strategies to improve walking function in patients with PD, and 2) understanding the dysfunction neural networks involved in FOG. The studies are innovative in that they: 1) determine the value of using tDCS as a conditioning intervention to modulate the excitability of the nervous system and thereby improve responsiveness to training, 2) seek non-pharmacological approaches for managing FOG and 3) explore the mechanism of action of tDCS on FOG.

Identifying noninvasive therapies for walking would bring a significant benefit for patients with PD, increase quality of life and decrease burden on caregivers. This research is relevant for the aging population in the United States and may be beneficial for patients with other neurological conditions such as frontal gait disorders, patients with white matter disease and cognitive impairment. Identifying the best stimulation parameters with the least side effects will set the stage for future clinical trials.

5) Inclusion and Exclusion Criteria

Patients with Parkinson's Disease as determined by the UK Brain Bank Criteria and Hoehn and Yahr (H&Y) stages 2-3 will be considered for enrollment. Patients will be screened at the University of Miami Movement Disorders Clinic by the Principal Investigator (PI) and his team.

Inclusion Criteria:

- Ages 18- 80
- Parkinson's Disease Hoehn and Yahr stages 2-3
- Presence of Freezing of Gait as per the freezing of gait questionnaire.

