Locomotor Training: The training paradigm will focus on strategies for which there is evidence of effectiveness in persons with PD. Briefly, during the first week, individuals practice the primary motor task, and motor dual tasks (DTs), receive frequent feedback and make use of auditory and visual cues. On the second week, cognitive-motor DTs are introduced and visual and auditory cues are decreased or removed in an effort to increase the challenge and to aid the individual in establishing an internal representation of the requirements necessary to carry out the walking training. Tasks increase in complexity in weeks 2 and 3 to promote transference of possible gains in gait performance to other motor behaviors found daily life without dependence on external stimuli.

11) Data and Specimen Banking

N/A

12) Data Management

We estimated the power based on a range of sample sizes, effect sizes at a 0.05 significance level with a two-sided t test. A total sample size of at least 40 PD patients will achieve at least 80% power to uncover an effect size of 0.94 at a significance level of 0.05 for a two-sided test. This effect size is corresponding to a mean difference of 15% (15.2cm/s) given that the square root of the within mean square error is 16. We performed the power analysis using PASS 2008 Software (NCSS, Kaysville, UT). For the data analysis, we will estimate the effect of tDCS on changes in gait velocity, TUG and UPDRS score using mix-effects models. All analyses will be conducted using SAS (version 9.2, SAS Institute Inc., Cary, NC).

All data files will be secured at the University of Miami. Data management will be monitored by the PI on an on-going basis.

Paper records:

Paper records will be housed in a locked file cabinet, in a locked room, with controlled access. Only the PI and associated research staff will have access to the records. Each participant will be assigned a unique study ID number. This ID is affixed to all data forms and is kept separate from the individual's identifying information, except in one electronic file which is password-protected and accessible only by the PI.

Study participants will not be specifically identified in any publication of the research results.

Records will be kept for 7 years after completion of the study, at which time they may be destroyed.

13) Provisions to Monitor the Data to Ensure the Safety of Subjects

Data Monitoring:

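### Section 12, Aims 2 and 3 and the conditioning claim name an effect of tDCS, but the one-arm pre-post design described can estimate only the change after combined tDCS and locomotor training

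*Combined protocol and SAP*

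**What the plan says.** **Design and contrast.** Sections 8 and 10 describe one sequence for everyone: baseline assessment, three weeks of locomotor training (nine sessions), then post-test. tDCS is given in each training session (Section 10, Intervention and Training Procedures). The Data Analysis part of Section 10 compares post-training with pre-training values by paired t-test. The available text describes no sham group, training-only group or allocation. Part of the document between Sections 21 and 26 was not available.

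**Places that name a tDCS-specific quantity.**
- Section 12, on the models: "we will estimate the effect of tDCS on changes in gait velocity, TUG and UPDRS score using mix-effects models".
- Section 3, Aim 2: "Quantify the effects of anodal direct current stimulation on cortical excitability of the motor cortex". The contrast given for it is pre-post only: "Transcranial magnetic stimulation (TMS) will be used to probe cortical excitability and plasticity of motor cortex pre and post intervention".
- Section 3, Aim 3: "Evaluate the cortical/subcortical changes induced by tDCS".
- Section 4, first innovation claim: "determine the value of using tDCS as a conditioning intervention to modulate the excitability of the nervous system and thereby improve responsiveness to training".

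**A mixed case.** Aim 1 opens with tDCS and then describes the combination: "Quantify the effects of tDCS on freezing of gait in patients with PD. tDCS will be administered together with locomotor training".

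**Places already worded for the combination.** The opening of Section 3 reads "We will test the effects of unilateral transcranial direct current stimulation (tDCS) in combination with locomotor training". The hypothesis in Section 4 and the feasibility sentence in Section 10 agree with it.

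**Power (Section 12).** At least 40 patients in total, at least 80% power, effect size 0.94, two-sided alpha 0.05. The effect size is tied to 15.2 cm/s and a root within mean square error of 16.

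**The concern.** What tDCS adds to training can be known only by comparison with training without tDCS, and the described design has no such comparison. The conditioning claim in Section 4 is the clearest case, because it concerns how far tDCS improves the response to training.

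The rival explanation comes from the protocol. Section 10 says the training uses strategies with evidence of effectiveness in PD. Potential Benefits to Subjects says gait training has improved gait parameters in earlier studies, while calling benefit in this study unknown. A gain in walking speed could therefore come from training, retesting or expectation. Under the Section 12 wording, that gain would carry the label of a tDCS effect on the primary outcome. The same applies to the TMS and MRS measures in Aims 2 and 3, which are repeated after three weeks of training.

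The power sentence adds a second question. Its arithmetic resembles that of a two-group comparison, so Section 12 may rest on a different design from Section 10.

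**Working it through.** **Inputs.** N = 40, d = 0.94, power at least 80%, two-sided alpha 0.05, difference 15.2 cm/s, SD 16 (all Section 12); paired t-test (Section 10). The documents do not say whether 16 is the SD of the pre-post change. Two readings are used: SD of change 16, or 16 × √2 = 22.6 if 16 is a within-person residual SD. No training-only gain is given, so that input is assumed.

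**1. The plan's power figure.** 15.2 / 16 = 0.95, close to the stated 0.94. Power comes from the noncentral t distribution.
- Two groups of n each: noncentrality = d × √(n/2), df = 2n − 2. For 20 versus 20: 0.94 × √10 = 2.97, df 38, power 82.6%. For 19 versus 19: 80.5%. For 18 versus 18: 78.2%.
- Paired, n = 40: noncentrality = d × √40, df = 39. At d = 0.94: 0.94 × 6.325 = 5.95, power over 99.9%.
- Paired, 15.2 cm/s with SD of change 22.6: d = 0.672, noncentrality 4.25, power 98.5%.

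A total of 40 for about 80% power thus matches two groups of 20. The paired test would reach 80% with 11 patients (d = 0.94), or with 20 if the SD of change is 22.6.

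**2. Identifiability.** Code intercept, time, training and tDCS for 40 patients at two visits. Time, training and tDCS are each 0 before and 1 after for every patient, so the three columns are identical and the design matrix has rank 2 out of 4. No mixed model or larger sample separates them. With a training-only group, the columns intercept, time and tDCS have full rank 3.

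**3. How often a gain unrelated to tDCS would be significant.** Assume that tDCS is inert and that other causes change speed by a fraction of 15.2 cm/s. Paired test, n = 40, noncentrality = (change / SD) × √40:

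| Assumed change | SD of change 16 | SD of change 22.6 |
|---|---|---|
| 3.8 cm/s (one quarter) | 31% | 18% |
| 7.6 cm/s (one half) | 83% | 54% |

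**4. What the paired test can detect.** With n = 40, 80% power corresponds to 0.454 SD of change: 0.454 × 16 = 7.3 cm/s, or 0.454 × 22.6 = 10.3 cm/s.

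**The case against.** **The operative text is mostly right.** The study calls itself a feasibility study, the opening objective and the hypothesis name the combination, and Section 10 defines every contrast as post versus pre. One arm and a paired t-test are valid for that change. All of this stands. It limits the fault to the places that name a tDCS-specific quantity, but Section 12 is analysis text and is one of them.

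**Section 12 has no reporting or success rule.** This also stands. That a gain will be reported as a tDCS effect is a forecast of how the named quantity will be read, not something the plan states.

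**The fault may be more than a label.** An effect on changes, together with the power arithmetic, reads naturally as a group contrast. A reader might infer that a two-arm trial was planned. No available passage mentions a second group, so the documents do not establish this. Equally, they do not show that the only fault is the name given to a time coefficient. The investigators have to say which design was meant.

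**The percentages rest on assumed gains.** They do, and smaller gains give smaller figures. The confounding in step 2 needs no assumed gain.

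**Background language is only rationale.** This is fair for the third innovation claim, "explore the mechanism of action of tDCS on FOG", which promises exploration and is left out of the required rewording. The conditioning claim promises to determine a value and stays in.

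**Conclusion.** The point holds for the design in the available text. The tDCS-specific effect named in Section 12, in Aims 2 and 3 and in the conditioning claim cannot be separated from training and time. This conclusion requires only that everyone receives tDCS in every session and is compared with baseline alone; it would need revisiting if the unavailable part describes a comparator. Even the combined pre-post change includes retesting and expectation.

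The ranges of 31% to 83% and 18% to 54% show how easily a result could be misread under assumed gains. They are neither bounds nor the trial's error rate: for its own null of no pre-post change, the paired test keeps 5%.

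Three stronger readings are not supported:
- A reader might infer that the study is underpowered. The paired test has at least 98.5% power for 15.2 cm/s under both SD readings, so the stated minimum of 80% is literally true.
- A reader might infer that the one-arm design is invalid. It is adequate for feasibility and for the combined change, and correcting the claim does not require a sham arm.
- A reader might take the two-group origin of the sample size as fact. It is inferred from the arithmetic.

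**What to change.** 1. Reconcile Sections 10 and 12 on the intended design, and state explicitly whether there is one group.
2. For the one-arm design as described, reword Section 12, Aims 1 to 3 and the conditioning claim in Section 4 to *change after combined tDCS and locomotor training*. Identify the time coefficient (post versus pre) in the Section 12 model as that change. Name either the paired t-test or the mixed model as primary for gait velocity. With two visits, complete data and a random participant intercept, the two give the same estimate and t statistic, so choosing one loses nothing.
3. State that no efficacy or mechanistic effect will be attributed to tDCS alone.
4. Restate power for the paired test with a named and justified SD of change, using the detectable change at 80% power: 7.3 cm/s if that SD is 16, or 10.3 cm/s if it is 22.6.

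If the one-arm design is confirmed, the cost is text edits and one restated power sentence. Participants, visits and sample size stay as they are. The study gives up a tDCS-specific conclusion that its data could not support, and keeps its feasibility and combined pre-post conclusions.

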Participants will qualify if they report 2 or more episodes of freezing per week

- Stable medication regimen
- Time to complete Timed up and go (TUG) between greater than 12 seconds

Exclusion criteria:

- Medical or orthopedic conditions that would interfere with gait training for 30 minutes
- Unable to perform timed up and go
- History of seizures
- Implanted deep brain stimulator, pacemaker or any other electronic device
- Dementia as defined by mini-mental state examination (MMSE) equal to or below 24
- Adults unable to consent, individuals who are not yet adults (infants, children, teenagers) pregnant women and prisoners will not be considered for participation

6) Number of Subjects

Forty subjects with PD and FOG will be recruited. Subjects with diagnosis of PD according with UK PD brain bank criteria, H &Y stage 2-3 and presence of FOG will be considered for the study.

7) Study-Wide Recruitment Methods

Potential subjects will be recruited from the clinics at the University of Miami-Movement Disorders Research Center, other health care providers in the Miami community and the local Miami community through support groups and public spaces. An experienced clinical trial team is currently in place to assure that the studies are conducted in a manner which allows for accurate, efficient and timely collection of data and provides a safe and pleasant environment for the patients. The Clinical Trial Staff have all received training and certification to conduct clinical trials from the University of Miami Research Administration and have been trained and currently follow Good Clinical Practice Guidelines to assure the safety and protection of study participants. The Center currently works closely with the National Parkinson Foundation and all of its local chapters and support groups to facilitate patient recruitment through multiple resources provided to the Center by the National Parkinson Foundation.

The study investigators will discuss the study with patients who have been diagnosed with Parkinson's Disease and meet the eligibility criteria. Patients with Parkinson's

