Disease H&Y stage 2-3, on a stable medication regimen and without major medical problems (i.e., cardiac problems, malignancy, h/o of seizures) will be candidates for the study. The subjects will be provided with an overview of the objectives and procedures, and with an informed consent form in their language. If patients agree to participate in the study a screening visit will be scheduled to assess the eligibility for participation.

8) Study Timelines

Each individual selected to participate will participate in a baseline evaluation visit, 9 training visits, and post-test evaluation visit. Evaluation visits are estimated to be 3 hours, and training visits 45minutes.

Visit #1- Pre-test assessment including gait, postural sway, cognition and TMS measures will be collected. Participants may divide this into two sessions, to accommodate for a shorter test duration.

Visit #2-9- Participants will participate in a 30 minute gait training protocol administered by trained personnel with tDCS augmentation. These visits will be scheduled 3 times per week for 3 weeks totaling 9 training sessions.

Visit #10- Post-test gait, postural sway, cognition and TMS measures will be collected. Participants may divide this into two sessions to accommodate for a shorter test duration.

We estimate the study will be completed in one year.

9) Study Endpoints

- Primary outcome change in walking speed
- Secondary outcomes are:
 - Freezing of gait: freezing of gait questionnaire, time spent with freezing of gait
 - Motor function: motor scores of Parkinson's Disease- UPDRS (part 3)
 - Locomotor function (biomechanical analysis [Gait Mobility Lab system]): 10 meter walk (speed and stride length), TUG (single and dual-task), postural control (postural sway)
 - Neurophysiological: motor threshold of the primary motor area as measured by TMS, and Glutamate/GABA ratio, as measured by MRS.
 - Neuropsychological: backward digit span, oral version of the trail making test, Montreal cognitive assessment (MOCA), and the consonant trigrams test

10) Procedures Involved

A feasibility study will be performed to evaluate the influence of tDCS in conjunction with locomotor training (LT) in participants with PD. Participants will undergo a battery

baseline assessments, followed by 3 weeks of locomotor training associated with tDCS. After training, participants will undergo a battery of post-test assessments.

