Data and safety monitoring will be the primary responsibility of the Co-Investigator, with on-going oversight by the study PI. All participant personal and medical information will be treated as confidential and safeguarded in accordance with the Privacy Act of 1974 and the Health Insurance Portability and Accountability Act of 1996 (HIPAA) which protects the privacy of individually identifiable health information, and identifiable information being used to analyze patient safety events and improve patient safety.

Safety:

Safety of participants will be monitored by the Co-Investigator on an on-going basis and reviewed by the study PI on a weekly basis. The study PI will be informed immediately of any suspected adverse effects.

All testing and training procedures will be performed by qualified personnel at the University of Miami Wellness Center (miller school of medicine and/or coral gables), which is located minutes from an emergency room.

In the event of a non-serious adverse reaction during participation in the study, a staff medical physician will be immediately paged or the participant will be escorted to the emergency room. In the event of an emergency, the EMS will be activated; first responders will immediately initiate basic emergency procedures and continue until EMS arrives.

Adverse effects reporting:

The principle investigator will comply with the required annual reporting of non-serious and serious adverse events to the IRB, General Clinical Research Center (GCRC), and Research Subject Advocacy (RSA) program of the University of Miami.

14) Withdrawal of Subjects

The following clinical criteria will be used for withdrawing a participant from the study: The principal investigator will withdraw participants who become ineligible to participate in the study (as per study inclusion and exclusion criteria), or if there is a safety concern for the participant or study investigators including seizure, pain or intolerable side effects.

15) Risks to Subjects

1) There is a risk of seizure associated with the use of transcranial magnetic stimulation (TMS), but this is considered remote (less than 1 in 10,000) provided that there is no history of: a) epilepsy; b) seizure; c) head injury, or d) stroke.

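### Section 14 takes people who lose eligibility or have a safety concern out of the study, not only out of training, and no post-test is described for them (low priority, cheap to fix)

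*Combined protocol and SAP*

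**What the plan says.** Section 14 (Withdrawal of Subjects) opens with "The following clinical criteria will be used for withdrawing a participant from the study" and then gives two grounds. The first is loss of eligibility: "The principal investigator will withdraw participants who become ineligible to participate in the study (as per study inclusion and exclusion criteria". The second is safety: "or if there is a safety concern for the participant or study investigators including seizure, pain or intolerable side effects".

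The criteria it points to are in Section 5. They include "Participants will qualify if they report 2 or more episodes of freezing per week", "Time to complete Timed up and go (TUG) between greater than 12 seconds" and, as an exclusion, "Unable to perform timed up and go". Section 4 gives the expected effect: "We hypothesize that tDCS in combination with locomotor training will reduce freezing of gait".

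Section 7 places the eligibility check before entry: "a screening visit will be scheduled to assess the eligibility for participation". Sections 8 and 10 schedule the outcome assessments at baseline and again once the three weeks of training are over. Section 10 compares pre with post by paired t-test. Section 12 adds mixed-effects models for gait velocity, TUG and UPDRS.

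**The concern.** The eligibility ground is mandatory, refers to a change after enrolment, and points to the whole entry list without naming a subset. Because safety is listed separately, the eligibility ground is not simply safety restated. One entry criterion, the weekly number of reported freezes, is something the intervention is meant to lower, so on a literal reading a good response would itself be a reason for removal.

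The wider point is that the section does not distinguish stopping tDCS and training from leaving follow-up. A participant who stops for pain, side effects or inability to train leaves the study too, with no post-test described.

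A paired t-test uses only people with both values, so each such person is lost for every outcome. The mixed models could keep the baseline, but the post value is still missing, and a baseline alone says nothing about that person's change. If loss is related to how people fare, the completers' mean change describes a selected subset of those enrolled. This is a single-group pre-post comparison, so no control arm offsets the selection.

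**Working it through.** **1. Which criteria could cause loss before the post-test?** Section 5 has 5 inclusion bullets and 6 exclusion bullets, 11 in all. Setting the effect-related ones beside the visit schedule:

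- *TUG longer than 12 s.* As an outcome, TUG is scheduled at baseline and post-test only. By the time an improved TUG is recorded, the post value exists. This criterion cannot cause loss of the post-test.
- *At least 2 reported freezes per week.* The freezing questionnaire is also scheduled only at baseline and post-test, and no count is scheduled at training visits. Loss would need an informal report during the 9 training sessions and an investigator who acted on it.
- *Unable to perform the TUG.* This could become evident during training, but it is mostly a proper reason to stop gait training. The open question is whether follow-up should stop too.
- *Safety ground.* This can arise at any training session. It is a proper reason to stop the intervention, with the same open question.

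**2. Is there a figure in the plan for this?** No. The text reviewed gives no loss rate, dropout allowance or missing-data rule. The nearest figures are the Section 12 power inputs: 40 patients, a difference of 15.2 cm/s and a root within mean square error of 16. These give 15.2/16 = 0.95 (15/16 = 0.9375, against the stated 0.94). The stated power of at least 80% reproduces as a two-group t-test with 20 per group and effect size 0.94, which gives 82.6%. The paired test in Section 10 with 40 people has more than 99.9% if the SD of change is 16. If 16 is instead a per-measurement SD, the SD of change is 16 × √2 = 22.6 and power is 98.5%.

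**3. Scale of a possible shift.** Let k of 40 have no post value, let C be the completers' mean change, and let L be the mean change the lost would have shown.

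Enrolled mean = [(40 − k) × C + k × L] / 40, so C − enrolled mean = (k/40) × (C − L).

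Both k and the gap C − L are assumptions; neither is in the documents.

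| k lost | Shift if gap is 8 cm/s | Shift if gap is 16 cm/s | As % of 15.2 |
|---|---|---|---|
| 0 | 0 | 0 | 0 |
| 1 | 0.2 | 0.4 | 1.3 to 2.6 |
| 2 | 0.4 | 0.8 | 2.6 to 5.3 |
| 4 | 0.8 | 1.6 | 5.3 to 10.5 |

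The sign depends on who is lost. Losing people who improved more than average lowers the completers' mean; losing people who did worse raises it.

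**4. Does power suffer?** Take the largest downward shift in the table: 36 completers and a mean of 15.2 − 1.6 = 13.6 cm/s. Two-sided paired t-test power at 0.05 is 99.9% with SD of change 16, and 93.9% with 22.6. What is at stake is whom the estimate describes, not the power of the primary test.

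**The case against.** The strongest reply is that the section was never meant this way. It calls its grounds clinical, Section 5 speaks of qualifying, Section 7 assigns eligibility to a screening visit, and no recheck is planned. Applied literally to all 11 bullets, the rule would also remove someone who turned 81 during the study. Withdrawing a patient because freezing improved would defeat the stated aim. All of this stands, and it makes loss through improvement unlikely. It does not change the wording, which is mandatory and unqualified and leaves the matter to whoever reads it.

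It can also be said that the lack of a post-test is inferred. Section 14 does not forbid one, and the text available for this review lacks the consent form and some text between the headings of Sections 21 and 26. That stands as a limit: the point is that no post-test is described for withdrawn participants in the text reviewed, not that none exists.

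A reader might go further and infer that the 12-second TUG limit would remove improvers. The visit schedule rules that out. A reader might also infer that the trial will lose its best responders and so understate the effect. With no scheduled recheck, and with stops for pain or inability pulling the other way, the documents support neither the frequency nor the direction. Assuming that 30% are withdrawn for improving, with a correlation of 0.7 between the withdrawal marker and walking-speed change and an SD of change of 22.6, the shift reaches 7.9 cm/s. Nothing in the documents supports that rate or that correlation.

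**Conclusion.** The point holds as a low-priority improvement. Section 14 merges stopping the intervention with leaving the study, and its eligibility ground is broad enough to include a criterion that the intervention is meant to change. If followed as written, it could make missing post-tests depend on response or tolerance.

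The bias cannot be sized from the documents and is zero if nobody is withdrawn before the post-test. The 0.2 to 1.6 cm/s range is illustrative and rests wholly on the assumed number lost and the assumed gap. Walking speed, the primary outcome, is not an entry criterion and is affected only indirectly. This does not threaten the main result.

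**What to change.** Amend Section 14 as follows:

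- State that the freezing-frequency and TUG criteria apply at screening only, so that a later change in either is not in itself a reason for withdrawal.
- Keep safety-based stopping of tDCS and training, including when gait training is no longer safe for that person.
- Separate stopping the intervention from leaving follow-up. Seek the post-test from every enrolled participant who agrees and can safely attend, covering at least the 10 m walk, TUG, FOGQ and UPDRS. TMS and MRS can be left out for those who stopped, particularly after a seizure.
- Analyse all available data from enrolled participants and report withdrawals by reason.

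The cost is a few sentences of protocol text and a few extra post-test visits for people who stopped training. Section 8 puts a full evaluation at about 3 hours and allows it to be split over two sessions; the minimum set above should take less. Some patients will decline or be unable to walk, so the change reduces missing data but will not remove it. No new staff or procedures are needed, and the sample size does not change.
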